9.2. Setting

The study is planned for one year duration. No formal calculation of sample size is provided. However, approximately 250 patients are planned to be screened and enrolled into the study from approximately 20 sites across India.

along with Allergan would identify the prescribing physicians strategically located throughout the whole country. Physicians who accept to participate must sign the Investigator Signature Page as an evidence of their approval.

- Study Visits: Visit 1/Baseline visit the site collects the following information: Informed consent
- Demography
- Medical history
- Concomitant medications
- Ophthalmic history
- Concomitant ophthalmic medications
- AEs/SAEs/adverse drug reactions (ADRs) (dates if available)
- Information on pregnancy (if applicable)
- Date of the last intravitreal Ozurdex[®] injection (if available)
- Date of the present intravitreal Ozurdex[®] injection

The AEs/SAEs/ADRs along with the date of the last intravitreal Ozurdex[®] injection w.r.t AEs and concomitant medications for the AEs will be collected in subsequent follow-up visits.

Patient Inclusion Criteria

- The patient has signed a written informed consent.
- Adult patient aged ≥ 18 years.
- The subject who is scheduled to receive at least one intravitreal Ozurdex[®] injection for the treatment of visual impairment due to DME.

Patient Exclusion Criteria

- Patients for whom Ozurdex is contraindicated:
 - Ocular or periocular infections
 - Glaucoma
 - Torn or ruptured posterior lens capsule
 - Hypersensitivity

9.3. Variables

Study Assessments:

• Written informed consent: Information about the program should be given in written form. Subjects, their relatives, guardians, if necessary legal representatives must be given ample opportunity to discuss any details of the program with the study

physician/investigator. Informed consent should be documented and signed by the patient before protocol-specified procedures are carried out.

- **Demography:** The following demographic details will be taken and recorded in the CRF Age, Gender, Date of Birth, Height and Weight.
- **Medical history:** Patients' relevant medical history pertaining to diabetes mellitus and its complications will be recorded. The following medical history details will be recorded in the CRF.

Name of the medical condition, type of the medical condition (if applicable), date of diagnosis of the medical condition, whether the medical condition is being treated or not, whether the medical condition is ongoing or stopped, if stopped, the stop date will be recorded. Any additional information about the complications arising due to diabetes mellitus will also be recorded as medical history.

• **Concomitant medications:** Patients relevant concomitant medications will be recorded. The following concomitant medication details will be recorded in the CRF.

Name of the concomitant medication, start date of the concomitant medication, whether the concomitant medication is ongoing or stopped, if stopped, the stop date will be recorded, reason for the intake of concomitant medication (indication for use), dose, unit and frequency.

• **Ophthalmic history:** Patients relevant ophthalmic history will be recorded. The following ophthalmic history details will be recorded in the CRF.

Name of the ophthalmic condition, date of diagnosis of the ophthalmic condition, whether the medical condition is being treated or not, whether the medical condition is ongoing or stopped, if stopped, the stop date will be recorded.

• **Concomitant ophthalmic medications:** Patients relevant concomitant ophthalmic medications will be recorded. The following concomitant ophthalmic medication details will be recorded in the CRF.

Name of the concomitant ophthalmic medication, start date of the concomitant ophthalmic medication, whether the concomitant ophthalmic medication is ongoing or stopped, if stopped, the stop date will be recorded, reason for the intake of concomitant ophthalmic medication (indication for use), dose, unit and frequency.

• **Information on pregnancy:** The following information will be recorded from the expecting female patients in the CRF at the initial visit.

Pregnancy status - Pregnant: Yes/No.

There is no requirement as part of the study to confirm pregnancies by a laboratory test.

Detailed information on pregnancy will be recorded and sent to Allergan either by fax or email mentioned in the page 1 of protocol by using Allergan pregnancy data communication form – Pre-delivery (initial) information. This form will be filled for all pregnancies in a female study patient or pregnancy in the partner of a male study patient.

During the subsequent visits, detailed information on follow-up (post-delivery) of pregnancy will be recorded and sent to Allergan either by fax or email mentioned in the page 1 of protocol by using Allergan pregnancy data communication form – Post-delivery (follow-up) information.

• **AEs/SAEs/ADRs:** The following details will be recorded in the CRF pertaining to AEs/SAEs/ADRs.

Verbatim term of the event, onset date of the event, resolution date of the event, seriousness, severity (mild, moderate, severe), outcome of the event, treatment for the event, relationship (related, not related) of the event to intravitreal Ozurdex[®] injection as judged by the study physician, action taken with respect to Ozurdex[®] will be recorded. Concomitant medications administered for the corresponding AE with details of start date, stop date, dose, unit and frequency will be captured.

Information on AEs/SAEs/ADRs will be recorded and sent to Allergan either by fax or email mentioned in the page 1 of protocol by using PMS AE form (SAE and non-serious ADR form).

• Date of the last intravitreal Ozurdex[®] injection: Date of the last dose of intravitreal Ozurdex[®] injection if available will be recorded.

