This study focuses on timely detection and characterization of serious and non-serious adverse events (AEs) including important identified and potential risks and AEs of special interest observed with intravitreal Ozurdex[®] injection for the treatment of visual impairment due to diabetic macular edema (DME) in the Indian population during usual clinical practice.

Ozurdex[®] (dexamethasone intravitreal implant) is a corticosteroid indicated for the treatment of macular edema following branch retinal vein occlusion (BRVO) or central retinal vein occlusion (CRVO); non-infectious uveitis affecting the posterior segment of the eye; and DME. Ozurdex[®] is an intravitreal implant containing 0.7 mg (700 mcg) dexamethasone in the Novadur[®] solid polymer sustained-release drug delivery system¹.

Diabetic macular edema

Diabetic eye disease (retinopathy) can damage the small blood vessels of the eye. Fluid leaking from these blood vessels may cause the central part of the retina (the macula) to swell. This is called DME. Diabetic macular edema is the most common cause of vision loss in people who have diabetes². Diabetic macular edema affects 20% of patients with diabetic retinopathy³. Diabetic macular edema is characterized by capillary leakage, fluid accumulation, and macular thickening following breakdown of the blood retinal barrier⁴. Inflammation plays a significant role in DME pathogenesis because the breakdown of the blood retinal barrier involves expression of inflammatory factors⁵ including vascular endothelial growth factor (VEGF), intercellular adhesion molecule-1, interleukin-6, monocyte chemotactic protein-1, leukostasis⁶ and alterations in endothelial tight junction proteins⁷.

India is second to China in having the maximum number of diabetics⁸. The International Diabetes Federation projects the increase in number of people with diabetes in India from 65.1 million in 2013 to 109 million in 2035⁹. This significant proportion of diabetes in India indicates an increase in diabetic retinopathy or DME cases. One risk factor for the development of diabetic retinopathy is hypertension associated with diabetes. The increase of such cases is directly proportional to the duration of diabetes. Proliferative diabetic retinopathy was seen in patients with 11 years of diabetes. Severe diabetic retinopathies were observed in 100% of patients with 25 years of diabetes¹⁰.

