9.1. Study design

This is an observational, prospective PMS program to evaluate the safety profile of intravitreal Ozurdex[®] by actively identifying and evaluating the occurrence of AEs and SAEs information.

Investigators will be trained on the conduct of the study by the Clinical Research Associate (CRA).

On the Visit 1/Baseline visit, an informed consent would be provided to the patients for obtaining consent to share the collected safety information for research purposes. No further visits are planned as it is at the discretion of the treating physician/investigator to schedule a follow-up (clinic visit/telephonic contact) with the patients. Refer to Annex 1 for sample informed consent form (ICF).

Following the signature on the ICF, the basic required information will be collected at Visit 1 by the study physician in a pre-designed case report form (CRF). The information collected at Visit 1 includes, patient demography characteristics, medical history, concomitant medications, ophthalmic history, concomitant ophthalmic medications, the date of the last intravitreal Ozurdex[®] injection if applicable, date of the present intravitreal Ozurdex[®] injection and AEs/SAEs at baseline if any (and the dates of AE/SAEs if available). Refer to Annex 1 for sample CRF.

No medication will be provided as part of the study as this is non-interventional and confers to usual clinical practice. However, the marketed intravitreal Ozurdex[®] injection could be administered to the patient at the discretion of the treating physician/investigator if he/she considers that it would be beneficial for the patient. The injection can be provided by the physician/investigator either in the same visit when informed consent was signed or in the subsequent visit. The date of the injection given will be recorded. Refer to Annex 1 for the Prescribing Information of Ozurdex[®] Intravitreal Implant for detailed Ozurdex[®] administration procedure. Patients who do not receive the injection will be replaced.

During the subsequent follow-up visits/telephonic contact, the study investigator will begin by querying for AEs by asking each subject a general, non-directed question such as "How have you been feeling since the last visit?" Investigator collects the information pertaining to AEs/SAEs and the dates of AE/SAEs if available, date of the last intravitreal Ozurdex[®] injection and other details entailing the safety information as mentioned in the pre-designed CRF.

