9.4. Data sources

Medical records of the patient will be used which serves as a data for determining exposures, effects and outcomes. Other variables such as potential confounding variables and effect modifiers will also be collected.

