9.9. Limitations of the research methods

This is an observational study aimed to collect and evaluate only the safety data. There is no hypothesis testing in the study to evaluate any statistical significance. Frequency of AE/SAEs will be calculated as appropriate. This is a single arm study where no comparisons are possible to assess causality. Incident and pre-existing safety event may not be able to be differentiated if the date of occurrence is not available. Information from this study would supplement safety data already available and is part of the regulatory commitment. As there is no study mandated visits or procedures, missing data could be observed to a large extent.

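### Section 9.3 limits medical history to diabetes and its complications, so an undated non-ocular condition that predates the study may be counted as a new AE

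*Protocol*

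**What the plan says.** The baseline systemic history is defined in Protocol section 9.3: "relevant medical history pertaining to diabetes mellitus and its complications will be recorded". The only extension goes in the same direction: "Any additional information about the complications arising due to diabetes mellitus will also be recorded as medical history". Sections 9.1 and 9.2 list medical history as a Visit 1 item without this limit, but section 9.3 says what goes into it. Ophthalmic history is a separate item and is not tied to diabetes.

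Other systemic disease can still reach the record in several ways:

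- **Medications (section 9.3).** "Patients relevant concomitant medications will be recorded", with start date and "reason for the intake of concomitant medication (indication for use), dose, unit and frequency".
- **Baseline events (sections 9.1 and 9.2).** AEs and SAEs present at Visit 1 are taken, with dates where these can be had.
- **Event record (section 9.3).** Each event has an onset-date field.
- **Verification (section 11.1).** Events on the CRF are checked against the medical record or with the treating doctor.

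Section 9.7 says that current medical conditions will be coded together with medical history, with no restriction to diabetes. Section 9.9 gives the relevant limitation: "Incident and pre-existing safety event may not be able to be differentiated if the date of occurrence is not available".

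**The concern.** The outcome and the baseline differ in scope. AE frequency, the main result of this program, covers any body system; the systemic history against which an event would be called new covers one disease and its consequences. When an onset date is missing, baseline history is the natural fallback for deciding whether a condition was already there. Section 9.3 removes that fallback for non-diabetic, non-ocular disease.

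The study has a single arm, so no comparison group would show the same misclassification and allow it to be discounted. A SAP cannot repair the gap either, because history that was not collected at entry cannot be recovered by an analysis rule.

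**Working it through.** The protocol states no figure on this point, so the check is a comparison of its sections.

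**Step 1: scope of the outcome.** Section 11.1 defines an AE as any unfavourable medical event and collects events whatever their cause. Section 9.7 calculates the frequency of AEs and SAEs over the study period.

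**Step 2: scope of the baseline.** Section 9.3 covers diabetes, its complications and relevant ophthalmic history. The history table itself is generic (condition, type, diagnosis date, treated or not, ongoing or stopped). The limit lies in the sentence that introduces the table, not in its structure.

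**Step 3: internal agreement.** Section 9.7 expects current medical conditions to be available for coding; section 9.3 does not ask for them beyond diabetes. The two should agree.

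**Step 4: what each indirect route misses.**

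| Route | Catches | Can miss |
|---|---|---|
| Medication indication and start date (9.3) | Treated disease | Untreated disease; drugs a site does not judge relevant |
| Baseline AEs/SAEs (9.1, 9.2) | Problems active at Visit 1 | A stable chronic condition that nobody would report as an event |
| Onset date (9.3) | Any event with a known date | Undated events; sections 9.1 and 9.2 ask for dates only where available |
| Record check (11.1) | Conditions visible in the chart or known to the treating doctor | Conditions in neither; also, section 9.3 lists no CRF item for pre-existing status |

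**Step 5: what is left.** A non-ocular condition is at risk of being counted as incident only if all of the following hold: it is not a complication of diabetes, it left no trace through medication or baseline events, it has no onset date when first reported, and the record check does not identify it as old. This is a narrower set than all non-diabetic disease, but it is not empty. Section 9.9 concedes the undated part and also expects missing data to be extensive, because no visits are mandated.

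**Step 6: size.** The count would be the number of patients multiplied by the proportions meeting each condition in step 5. The protocol supplies only the first factor (about 250). No comorbidity rate, late-mention rate or missing-date rate is given, so no count or percentage follows.

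**The case against.** The strongest reply is that lean systemic history is a defensible choice in a non-interventional program for an intravitreal product. Ocular events are unaffected, the indirect routes catch much of the rest, and section 9.9 discloses the limitation. The introductory sentence in section 9.3 does not say that only diabetic history may be entered, and the sample CRF listed in Annex 1 is not shown, so the actual form may be broader. Most of this stands, and it keeps the point small. It does not remove it: the routes are partial, and a disclosed limitation that a wording change would reduce is still worth reducing.

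A reader might infer more than the protocol supports:

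- **That other systemic disease is not documented at entry at all.** Too absolute, given the medication and baseline-event routes.
- **That SAE frequency is inflated.** A long-standing condition merely mentioned late would rarely meet the seriousness criteria in section 11.1, and a hospitalization during follow-up is an in-study event whatever the history says.
- **That pre-planned procedures are left uncovered.** Section 11.1 already requires them to be documented in the source documents at entry.
- **That confounders go uncollected.** Section 9.4 says the opposite: "Other variables such as potential confounding variables and effect modifiers will also be collected". It does not list them, so non-collection would be a guess.
- **That hypertension is excluded.** Section 7 reads "One risk factor for the development of diabetic retinopathy is hypertension associated with diabetes", and hypertension so described plausibly falls within history pertaining to diabetes.
- **That the relatedness judgement is undermined.** It is made by the study physician, who holds the patient's records; the CRF's scope does not limit what that physician knows.

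**Conclusion.** The point holds in a limited form. The history rule in section 9.3 is narrower than the AE collection it has to support and narrower than the coding plan in section 9.7. As a result, an undated, non-ocular, non-diabetic condition that was untreated or unrecorded at Visit 1 may enter the AE frequency as new. Misclassification is possible, not automatic.

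Its size is unknown. Any number of affected patients would rest on assumed rates, and would further assume that the date and record checks fail and that the patient has no other AE, since otherwise the proportion of patients with an AE would not change. The conclusion takes section 9.3 as the operative definition of the CRF content. If the CRF is already broader, the remaining task is to bring the text into line with it.

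**What to change.** In section 9.3, replace the diabetes-only wording with an instruction to record all relevant past and ongoing medical conditions of any body system, including diabetes mellitus and its complications. Use the existing CRF history table. Where the diagnosis date is unknown, allow an entry stating that the condition was present before Visit 1. This brings section 9.3 into agreement with section 9.7 and gives a basis for classifying undated events.

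The rule for counting an event as new or worsened can be left to the SAP; it needs only that the baseline information exists.

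Cost: a wording change, a check that the CRF and its completion instructions match, and a few more rows per patient at Visit 1. No added visit or procedure is needed.

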9.4. Data sources

Medical records of the patient will be used which serves as a data for determining exposures, effects and outcomes. Other variables such as potential confounding variables and effect modifiers will also be collected.

9.5. Study size

No formal sample size calculation is performed since this is an observational, prospective, noninterventional study without a comparison group and the goal is to evaluate the usual clinical practice experience with Ozurdex[®] in all the eligible patients. Approximately 250 patients are planned to be enrolled into the study from 20 sites across India based on the enrollment potential and is considered a representative sample.

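### Section 9.5 calls the sample representative on feasibility grounds alone, and the protocol describes neither consecutive invitation nor a log that would show selection

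*Protocol*

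**What the plan says.** Protocol section 9.5 gives the aim and the size together. On the aim, "the goal is to evaluate the usual clinical practice experience with Ozurdex[®] in all the eligible patients". On the size, it states that "No formal sample size calculation is performed since this is an observational, prospective, noninterventional study without a comparison group", and then sets about 250 patients from 20 sites, "based on the enrollment potential and is considered a representative sample".

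Section 9.2 describes how sites and patients come in. Another party (its name is blank in the text) together with the sponsor "would identify the prescribing physicians strategically located throughout the whole country". Participation is voluntary: "Physicians who accept to participate must sign the Investigator Signature Page". For patients, "approximately 250 patients are planned to be screened and enrolled into the study from approximately 20 sites across India". Apart from consent, adult age and the listed contraindications, the entry condition is: "The subject who is scheduled to receive at least one intravitreal Ozurdex[®] injection for the treatment of visual impairment due to DME". The order in which eligible patients are approached is not stated.

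Section 9.10.2 asks sites to keep a record for each patient who is enrolled. Section 9.9 lists the single arm, undated events and possibly extensive missing data as limitations. It does not mention selection of sites or patients.

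**The concern.** Section 9.5 asserts a property of the sample and offers recruitment capacity as the only reason for it. How many patients 20 sites can recruit says nothing about whether those patients resemble the eligible patients who were not recruited. The same section names every eligible patient as the population of interest, and no rule in the protocol links the two.

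The main output of this single-arm study is the frequency of AEs and SAEs. With no comparator, that frequency is only as informative as the answer to the question of whom it describes. Section 12.1 sends the final report to the agency for expert committee evaluation. If representativeness is stated as fact and eligible patients left out go unrecorded, the committee cannot tell whether the frequencies run high or low. The gap cannot be closed afterwards, because counts of patients not enrolled have to be kept while enrolment is running.

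**Working it through.** **1. Can the figure of 250 be reproduced?** No. The protocol gives no event rate, precision target, alpha or power, and says openly that there is no formal calculation. That is acceptable for descriptive surveillance and is not the point here. The only arithmetic available is 250 / 20 = 12.5 patients per site on average.

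**2. Does the size itself support the claim?** It supports precision only.
- With 0 events in 250, the one-sided 95% upper bound is 1 − 0.05^(1/250) = 1.19%.
- With 25 events in 250 (10%), the exact 95% interval is 6.6% to 14.4%.

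These limits describe random error on the assumption that the sample is unbiased. They do not test that assumption.

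**3. Does anything else in the protocol support it?**

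| What would support the claim | What the protocol describes |
|---|---|
| A sampling frame or stated selection criteria for sites | Purposive identification of prescribers, intended country-wide spread, voluntary acceptance (9.2) |
| Invitation of every, or every consecutive, eligible patient | No statement on order or completeness of invitation (9.1, 9.2) |
| A count of eligible patients not enrolled | One figure, about 250, for both screened and enrolled (9.2); records required for enrolled patients (9.10.2) |
| An acknowledged limitation | Selection not listed (9.9) |

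**4. What could selection do?** Let f be the enrolled fraction of eligible patients, p_e the AE risk in those enrolled and p_n the risk in those not enrolled. The risk among all eligible patients is f·p_e + (1 − f)·p_n, so the error in the observed frequency is (1 − f)(p_e − p_n). The rates below are assumed; none is in the protocol. With p_e = 10%:

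| f | p_n = 15% | p_n = 20% |
|---|---|---|
| 0.75 | 11.3% | 12.5% |
| 0.50 | 12.5% | 15.0% |
| 0.25 | 13.8% | 17.5% |

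**5. Direction.** Assume 40% of eligible patients carry 30% AE risk and 60% carry 15%. The true frequency is 0.4 × 0.30 + 0.6 × 0.15 = 21.0%.
- Higher-risk patients approached half as often: their share is 0.2 / (0.2 + 0.6) = 0.25, and the frequency is 0.25 × 0.30 + 0.75 × 0.15 = 18.75%.
- Lower-risk patients approached half as often: the higher-risk share is 0.4 / (0.4 + 0.3) = 0.571, and the frequency is 0.571 × 0.30 + 0.429 × 0.15 = 23.6%.

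The error can take either sign. The formula in step 4 also shows why the enrolled fraction matters: for a given difference in risk, the error shrinks in proportion to 1 − f. Nothing the protocol plans to record allows f to be calculated.

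**The case against.** The strongest case on the other side is that this is a modest descriptive study that claims little. Section 9.7 confines frequencies to study participants, section 9.9 says the data supplement what is already known, and no hypothesis is tested. Baseline demography, history and prior implant dates are collected, so the case mix of enrolled patients can be described. Sites are meant to be spread across the country. The illustrated downward shift, 21.0 − 18.75 = 2.25 points, is less than half the approximate 95% half-width at n = 250, which is 1.96 × √(0.21 × 0.79 / 250) = 5.0 points. A log of people who have not consented is also a new procedure.

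Much of this stands. It limits the harm, and it is why the log proposed below is anonymous and count-level. It does not rescue the wording of section 9.5. Describing enrolled patients does not show how they differ from those left out, geographic spread does not govern who is invited within a site, and a sampling interval does not cover selection.

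Stronger readings are tempting, but the document does not support them:
- *Patients are enrolled non-consecutively.* The protocol is silent on order, and the stated aim of covering every eligible patient points, if anything, the other way.
- *The sponsor alone hand-picks sites.* Identification is shared with another party, and physicians may decline.
- *The physician's discretion in section 9.1 shows selective enrolment.* That text concerns the decision to inject, not who is invited into the study.
- *No screening record exists.* The data management plan, the site management plans and the sample CRF are not shown and could contain one.
- *AE frequency is biased low.* Neither sign nor size follows from the document.

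**Conclusion.** The point holds in a limited form. Section 9.5 states that the sample is representative, the only basis given is feasibility, and the protocol describes no invitation rule, no log and no limitation that would support or qualify the statement. Any resulting bias in AE and SAE frequency may go either way, and its size cannot be estimated from the document; the figures in the working rest wholly on assumed rates and show only the mechanism. The conclusion about detectability covers what this protocol describes and not operational documents that may add to it. The absence of a formal sample size calculation is disclosed and is not part of the criticism. This is an inexpensive correction worth making before enrolment, and it does not invalidate the study.

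**What to change.** 1. **Sections 9.1 and 9.2:** require each site to invite consecutive eligible patients scheduled for an injection until enrolment closes.
2. **Same sections:** have each site keep a minimal anonymous count-level log of eligible patients (enrolled, declined, or not approached, with the reason), subject to ethics committee agreement. If an operational document already provides for such a log, refer to it.
3. **Report:** give the enrolled fraction by site.
4. **Section 9.5:** replace the statement of representativeness with wording such as *a feasibility-based sample; representativeness will be judged from the screening log*.
5. **Section 9.9:** add selection bias. This should cover site selection as well, because a patient log says nothing about physicians who were not identified or who declined.

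The cost is minor paperwork at an average of 12.5 enrolled patients per site, a point to raise with the ethics committees, and a weaker claim in the report. No treatment, visit or patient procedure changes. The log will not prove representativeness; it will show how much room there is for selection.
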